**6.2 Number of subjects**

[REDACTED]

Up to 54 individuals will be enrolled as subjects and randomized to either Group #1 or Group #2 using a 1:1 randomization scheme. A total of up to 54 subjects (27 subjects per group) will undergo lead placement. [REDACTED]

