**9.1 Primary clinical efficacy endpoint analysis**

[REDACTED]

The effectiveness of percutaneous Peripheral Nerve Stimulation (PNS) for the treatment of post-amputation pain will be assessed in the present study. The goal of the proposed [REDACTED] study is to determine if the investigational treatment produces pain relief that is clinically meaningful and greater than the placebo effect. To distinguish between the effect of the investigational treatment and the placebo effect, qualifying individuals will be randomized (1:1) to either Group #1 (Treatment) or Group #2 (Control). The groups will be identical except for whether active stimulation (Group #1) or sham stimulation (Group #2) is delivered during the first 4 weeks of the home trial. Both groups are expected to experience a similar placebo effect from the study procedures and use of the devices. In Group #1, subjects will experience both the placebo effect and the investigational treatment effect. During the sham stimulation phase in Group #2, subjects will experience only the placebo effect. Thus, if there is a difference between the mean improvements during sham stimulation and active stimulation, it can be attributed to the investigational treatment effects.

The null hypothesis ( $H_0$ ) is that the investigational treatment (Group #1, active simulation) is equal to the control (Group #2, sham stimulation) in providing pain relief. The alternative hypothesis ( $H_1$ ) is that Group #1 has a proportion of successes that is not equal to the proportion of successes of Group #2.

1.  $H_0$ : proportion of successes of Group #1 = proportion of successes of Group #2
2.  $H_1$ : proportion of successes of Group #1  $\neq$  proportion of successes of Group #2

If the proportion of successes of the investigational treatment is statistically significantly greater ( $p < 0.05$ ) than the proportion of successes of the control during the first 4 weeks of the home trial and the alternative hypothesis is accepted at the 0.05 level of significance, it will indicate that the investigational treatment is clinically significant and different than the placebo effect.

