The following variables: sex, age, baseline pain intensity, time elapsed from amputation, medications affecting pain used at baseline, prosthesis fit, baseline BDI-II score, and percent changes in usage of medication affecting pain between baseline and EOT (i.e., PRN medication usage) will be examined via a covariate analysis to determine their influence on the primary outcome.

**9.1.2 A power analysis of the 2-tailed, 2-sample Mann-Whitney test was conducted for the primary efficacy endpoint to determine the sample size for > 90% power and a 5% significance level**

A power analysis of the 2-tailed, 2-sample Mann-Whitney test was conducted with data from the previous feasibility study and data published in other studies. The proportion of successes expected for Group #1 was estimated from the previous feasibility study in which stimulation produced comfortable sensations (paresthesia) in the region of greatest pain. The proportion of successes expected for Group #2 was estimated from published studies in which sham (placebo) treatments were given to amputees with post-amputation pain. The null hypothesis that the proportion of successes of Group #1 is equal to the proportion of successes of Group #2 was tested.

[REDACTED]

[REDACTED]

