### 9.3 Secondary clinical efficacy endpoint analysis

Additional endpoints below will be assessed to document further the effectiveness of using the SPRINT Peripheral Nerve Stimulation (PNS) System for the symptomatic relief and management of post-amputation pain.

- Durability of the treatment effect on average pain intensity (Primary Endpoint) after 8-week home trial

The durability of the treatment effect on average pain intensity compares the proportion of subjects who successfully achieve  $\geq 50\%$  reduction from baseline in Group #1 at end of 8-week home trial relative to that in Group #2 at end of 4-week sham period, examining the statistical superiority of the proportion of successes of Group #1 over the proportion of successes of Group #2. The post-amputation pain intensity scores will be determined for each subject by applying the same method used for the primary endpoint: taking the mean of the daily average pain intensity (BPI-SF Question #5) reported in the 7-day diary at baseline compared to the mean score for the same region(s) of pain reported over the 8 weeks of treatment (*i.e.*, the average of all scores in the diaries during this period) for Group #1. To be

considered a success, subjects must have  $\geq 50\%$  reduction in all qualifying regions of pain, defined as regions of RLP and PLP with a baseline pain score  $\geq 4$  that received blinded treatment. The proportion of successes in Group #1 will be compared to the proportion of successes in Group #2 during the sham stimulation phase (Weeks 1-4 of the home trial). The null hypothesis is that there is no difference in success rates between the two treatment groups, versus the alternative hypothesis, that the success rates differ from one another.

- Durability of the treatment effect on average pain intensity (Primary Endpoint) at monthly intervals after start of therapy (3 - 12 months after start)

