The analysis of the durability of the treatment effect on average pain intensity compares the proportion of subjects who successfully achieve  $\geq 30\%$  reduction from baseline in Group #1 relative to that in Group #2, examining the statistical superiority of the proportion of successes of Group #1 over the proportion of successes of Group #2. The average post-amputation pain intensity scores will be determined for each subject using BPI-SF Question #5 with 1 week recall. For Group #1, the scores reported at Visit 2 (prior to lead placement) will be compared to the score for the same region(s) of pain at each monthly interval after the end of the 8-week home trial (i.e., during the monthly follow-up calls/visits from months 3-12 after start of therapy). For Group #2, the scores reported at Visit 2 (prior to lead placement) will be compared to the score for the same region(s) of pain during the final week of the 4-week sham period. To be considered a success, subjects must have clinically-significant reduction ( $\geq 30\%$ ) from baseline in all qualifying regions of pain, defined as regions of RLP and PLP with a baseline pain score  $\geq 4$  that received blinded treatment. The proportion of successes in Group #1 at each monthly visit will be compared to the proportion of successes in Group #2 at the end of the sham period. For each month, the null hypothesis is that there is no difference in success rates between the two treatment groups, versus the alternative hypothesis, that the success rates differ from one another. Testing will be conducted at the 0.05 level of significance.

- Pain interference (BPI-SF Question #9) at monthly intervals after start of therapy

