The analysis of the treatment effect on pain interference compares the proportion of subjects who successfully achieve  $\geq 50\%$  reduction in average pain interference score in Group #1 relative to that in Group #2, examining the statistical superiority of the proportion of successes of Group #1 to that of Group #2. In Group #1, the baseline average pain interference score (BPI-SF Question #9) will be compared to the average pain interference score for the same region(s) at each monthly interval after start of therapy. In Group #2, the baseline average pain interference score will be compared to the score at the end of the 4-week sham period. To be considered a success, subjects must have  $\geq 50\%$  reduction in the average pain interference score of all qualifying regions of pain, defined as regions of RLP and PLP with an average baseline pain interference score  $\geq 4$  that received blinded treatment. The null hypothesis is that there is no difference in success rates between the two treatment groups (i.e., Group #1 at the monthly interval vs. Group #2 at end of sham period), versus the alternative hypothesis, that the success rates differ from one another. Testing will be conducted at the 0.05 level of significance.

- Pain disability (Pain Disability Index (PDI)) at monthly intervals after start of therapy

The analysis of treatment effect on pain disability compares the proportion of subjects who successfully achieve  $\geq 10$  point reduction in PDI scores from baseline in Group #1 relative to that of Group #2, examining the statistical superiority of the proportion of successes of Group #1 to that of Group #2. The baseline PDI score will be compared to the PDI score at end of first 4 weeks, at the end of the home trial, and at monthly intervals after end of therapy (3-12 months after start of therapy). In Group #1, the baseline PDI score will be compared to the PDI score at each monthly interval after start of therapy. In Group #2, the baseline PDI score will be compared to the score at the end of the 4-week sham period. To be considered a success, subjects must have a  $\geq 10$  point reduction in PDI. The null hypothesis is that there is no difference in success rates between the two treatment groups (*i.e.*, Group #1 at the monthly interval vs. Group #2 at end of sham period), versus the alternative hypothesis, that the success rates differ from one another. Testing will be conducted at the 0.05 level of significance.

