### 9.5 Per Protocol and Intent to Treat Analyses

Analyses of the primary and secondary effectiveness endpoints will be conducted on the intent-to-treat (ITT) population and the per-protocol (PP) population at each specified study interval defined as follows:

PP Population: The per-protocol population will consist of all randomized subjects who meet the following criteria:

- Were implanted [REDACTED]
- For Group #1 subjects: paresthesia coverage in the target areas.
- Have an adequate number of average pain intensity (BPI-5) scores in the diaries during the primary endpoint period (*i.e.*, first 4 weeks of home trial). These diaries must not be missing more than 50% of the pain scores to be included in the PP population.

[REDACTED]

- Continued study eligibility (subjects cannot have a change in medical status that would have otherwise excluded them from the study)

ITT Population: The intent-to-treat population will include all randomized patients who were implanted [REDACTED] that is, patients will be analyzed according to the treatment group to which they were randomized. Evaluable subjects are defined as those who were randomized and implanted with a lead.

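### Section 9.3 plans up to about 51 secondary comparisons, mostly repeated months against one sham value, with no visible gate, order or multiplicity adjustment

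*Combined protocol and SAP*

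**What the plan says.** Section 9.3 (Secondary clinical efficacy endpoint analysis) sets out seven tested secondary measures.

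- **8-week pain durability.** The success proportion is compared "in Group #1 at end of 8-week home trial relative to that in Group #2 at end of 4-week sham period". Hypotheses are given, but no significance level.
- **Monthly pain durability, months 3 to 12.** Each month has its own hypothesis: "For each month, the null hypothesis is that there is no difference in success rates between the two treatment groups". Every month of Group #1 is set against Group #2 at the end of sham.
- **Pain interference, PDI and BDI-II.** Each is compared at monthly intervals in Group #1, again against Group #2's end-of-sham value.
- **Opioid use and prosthetic use.** Each is compared at week 4 and at week 8, with hypotheses but no significance level.

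The monthly durability, interference, PDI and BDI-II paragraphs each carry the sentence "Testing will be conducted at the 0.05 level of significance". Most of the measures are described as examining the statistical superiority of Group #1. Section 9.5 adds that "Analyses of the primary and secondary effectiveness endpoints will be conducted on the intent-to-treat (ITT) population and the per-protocol (PP) population". The visible text does not say which population decides.

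For the primary endpoint, section 9.1 concludes in favour of treatment if "the alternative hypothesis is accepted at the 0.05 level of significance". No visible text makes a secondary test depend on that result, orders the secondary tests, adjusts their level or names a key month.

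**The concern.** Each monthly comparison is written as a free-standing superiority test at the full 0.05. With several measures and up to 12 time points each, a study with no true effect has many chances to produce a significant secondary result, and the plan as visible would let any of them be reported as superiority.

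The months are also not separate pieces of evidence. They come from the same Group #1 subjects and share one Group #2 value per endpoint. If the sham value happens to be low, many months turn significant together. A reader would see that run as repeated confirmation that the effect lasts, when it may reflect a single chance result in the control group.

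**Working it through.** **The plan's own figure.** The documents give no count of secondary tests and no family-wise error rate. Their only design calculation concerns the primary: "A power analysis of the 2-tailed, 2-sample Mann-Whitney test was conducted with data from the previous feasibility study", "to determine the sample size for > 90% power and a 5% significance level". The assumed success rates are redacted. By the normal approximation without continuity correction, 27 per group gives 90% power at, for example, 10% vs 49%, 20% vs 62% or 30% vs 73%. The sample size can be neither confirmed nor refuted, and the present point does not depend on it.

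**Inputs from the documents.**
- Group size: "A total of up to 54 subjects (27 subjects per group) will undergo lead placement" (section 6.2).
- Direction: the power analysis is two-tailed and the secondary alternatives are that the groups differ, so one test at 0.05 carries 0.05 / 2 = 2.5% in favour of Group #1.

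**Count of comparisons.**
- 8-week durability: 1
- Monthly durability, months 3 to 12: 10
- Interference, months 1 to 12: 12 (assumed)
- PDI, week 4, end of home trial and months 3 to 12: 2 + 10 = 12
- BDI-II, months 1 to 12: 12 (assumed)
- Opioid use: 2
- Prosthetic use: 2

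Total: 1 + 10 + 12 + 12 + 12 + 2 + 2 = 51. Those with 0.05 written beside them: 10 + 12 + 12 + 12 = 46. The remaining five state no level. If interference and BDI-II were collected only at the five clinic time points (weeks 4 and 8; 1, 4 and 10 months after end of treatment), the total would be 51 − 7 − 7 = 37.

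**Reference value under independence.** 1 − 0.95^51 = 92.7% in either direction; 1 − 0.975^51 = 72.5% favouring Group #1. For 46 tests: 90.6% and 68.8%. Independence does not hold here, so these are outer limits only.

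**Simulation with no true effect.** There are 27 subjects per group. Each subject has a component shared across endpoints, a component shared within an endpoint, and a residual. Group #2 supplies one value per endpoint, reused against every Group #1 time point. Durability, interference and PDI are analysed as success proportions by chi-square or Fisher, and the rest by t-test; some runs treat every endpoint as continuous. The correlations and the 20 to 30% success rates are assumptions. Section 9.3 does not name the test for proportions, so both are shown. Two simplifications: the 8-week durability test is pooled with the monthly ones, and all 27 subjects contribute to opioid use.

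| Setting | At least one false result favouring Group #1 | Either direction |
|---|---|---|
| 51 tests, shared sham value, no other correlation | 40–55% | 66–84% |
| 51 tests, within-endpoint 0.3–0.9, between 0.1–0.7 | 14–47% | 27–79% |
| 51 tests, within 0.7, between 0.3–0.5 | 20–34% | 40–66% |
| 46 tests (four monthly measures, all as proportions), within 0.3–0.9, between 0.1–0.7 | 9–44% | 20–76% |
| 37 tests, within 0.6–0.8, between 0.4 | 18–32% | 37–63% |

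For the ten monthly pain tests alone, the chance of a false result favouring Group #1 is about 3–7% (Fisher) or 6–14% (chi-square).

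**Clustering.** The mean number of false results among affected trials is the overall mean divided by the chance of any. With all endpoints continuous, within 0.3 and between 0.1 give 1.21 / 0.42 = 2.9. Within 0.9 and between 0.7 give 1.526 / 0.147 = 10.4. Higher correlation makes a false finding rarer but turns it into a long run.

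**The case against.** The study calls itself a pilot. Section 4.4 presents the secondary endpoints as a way to learn what the interventions do to each measure, and the visible rule for concluding that treatment differs from placebo rests on the primary alone. No visible text makes a secondary or per-protocol result a route to trial success. This stands and lowers the weight of the point. It does not remove it: section 9.3 says these endpoints are there to document effectiveness further, and it repeats superiority wording and a 0.05 level measure by measure.

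Stronger readings are tempting, and the documents do not support them.

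- A reader might infer that a false superiority claim is likely, or put it at 93%. That figure assumes independence and counts results in both directions. In favour of Group #1 the chance stays below even odds under every assumed correlation; it passes 50% only near independence.
- A reader might infer that every secondary test uses 0.05. It is written for 46 of the 51.
- A reader might take 51 as the plan's number. It assumes monthly collection of interference and BDI-II. Seven of the ten follow-up contacts from month 3 on are telephone calls, their content is redacted, and the Appendix A schedule is not visible.
- A reader might infer that the plan has no gate at all. Parts of sections 4.4, 9.0 and 9.1 are redacted, so the most that can be said is that none is visible.
- A reader might double the count to 102 because both populations are analysed. Listing ITT and per-protocol analyses does not by itself double the claims.

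It is also fair to say that ordering the tests does not cure the shared comparator: one low sham value can carry every month through a sequence. That follows from Group #2 starting active stimulation after week 4, and it needs a statement of its own.

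**Conclusion.** The point holds as a gap in error control for the secondary claims; the primary test is unaffected. On the visible text, up to about 51 secondary comparisons, 46 of them explicitly at 0.05, have no gate, order or adjustment. The chance of at least one false result favouring Group #1 is roughly 9 to 47%, against a nominal 2.5%, or about 4 to 19 times as high (9 / 2.5 = 3.6; 47 / 2.5 = 18.8).

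The range rests on assumed correlations and success rates that are not in the documents, and the count on an assumed monthly schedule. The conclusion does not need the exact count: with 37 tests the chance is still 18 to 32%. For the monthly pain tests taken alone the inflation is modest. The plan should either control these tests or describe them as descriptive; at present it visibly does neither.

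**What to change.** Amend sections 9.3 and 9.5 as follows.

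1. Test secondary superiority only if the primary is significant in favour of Group #1 in the ITT population.
2. Test pain durability in a fixed sequence: 8 weeks, then months 3 to 12 in order, each at two-sided 0.05, stopping at the first p ≥ 0.05.
3. Report all other secondary results, and all per-protocol results, descriptively with 95% confidence intervals and without superiority wording.
4. State that the monthly comparisons share one Group #2 sham value, so a run of significant months is not independent confirmation.

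Items 1 and 2 hold the family-wise error of the formal claims at or below 0.05 two-sided, 0.025 in favour of Group #1. Splitting the level equally would instead need 0.05 / 51 = 0.00098 per test, a very strict threshold for 27 per group.

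The change is wording only and needs no new subjects, visits or data. The price is that later months cannot be claimed once an earlier one fails, and that the other secondaries support no formal claim. Item 4 discloses the shared comparator but does not remove it.

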**Number of Subjects**

Up to 54 individuals will be enrolled. Using a 1:1 randomization scheme, subjects will be randomized to either Group #1 (Treatment) or Group #2 (Control).

|  |   |
|--|---|
| 
Inclusion Criteria
(assessed at Eligibility Visit 1)
                | 
 
• At least 18 years old
 
• Traumatic lower extremity amputation(s)
 
• Healed amputation and healthy residual limb based upon the investigator's evaluation
 
• Post-amputation pain [REDACTED] despite receiving at least two conservative therapies
 
• Able to understand and willing to take part in study and comply with all study requirements
 
  |
| 
Additional Inclusion Criteria
(assessed prior to the Testing Visit)
 | 
 
• Average post-amputation pain [REDACTED]
 
   |
| 
Exclusion Criteria
   | 
 
• Change of prescribed medications affecting pain [REDACTED] as indicated from subject-reported medication history.
 
• Beck Depression Inventory (BDI-II) score of > 20
 
• Compromised immune system based on medical history [REDACTED]
 
• Diabetes Mellitus Types I or II from medical history or subject reported history
 
• Implanted spinal cord stimulator, cardiac pacemaker/defibrillator or Deep Brain Stimulator
 
• History of bleeding disorder [REDACTED]
 
• History of valvular heart disease
 
• Confounding central nervous system injuries and disorders [REDACTED]
 
• Allergy to all local anesthetic agents [REDACTED]
 
• Allergy to skin-contact materials [REDACTED]
 
• History of recurrent skin infections
 
• Botulinum toxin injection within the last three months in the affected limb
 
• Steroid injection within the last six weeks in the affected limb
 
• Subject has participated in any drug or device trial in the past 30 days
 
• Subject has participated in previous [REDACTED] Amputee Pain feasibility trial
 
• Any other condition that may interfere with the ability to participate in a clinical trial [REDACTED] as determined by the Investigator
 
• Prisoners
 
 |

|   |   |
|---|---|

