**9.0 Outcome analysis**

All primary and secondary endpoint data will be analyzed and reported. This study is a randomized placebo-controlled [REDACTED] study. The goal of the study is to gather data regarding the safety and effectiveness of percutaneous PNS for the treatment of post-amputation pain. Descriptive statistics will be used to summarize baseline subject characteristics within each treatment group. Baseline characteristics include both demographic variables as well as variables such as baseline pain intensity, time elapsed from amputation, medications affecting pain used at baseline, prosthesis fit, and the baseline BDI-II score. These characteristics will be examined via a covariate analysis.

[REDACTED]

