Pain relief will be evaluated using the average pain intensity. All regions of post-amputation pain (RLP or PLP or both) that have intensities  $\geq 4$  on average during the baseline period and receive treatment with an investigational device will be used to assess the primary efficacy endpoint. All amputees will record two daily post-amputation pain scores (one daily score for RLP and one daily score for PLP) for each amputated leg in the 7-day diaries using BPI-SF Question #5. For each individual, the region(s) of post-amputation pain with a 7-day average  $\geq 4$  during baseline in a leg that receives blinded treatment from an investigational device(s) will qualify to be used in the determination of clinically-meaningful success for that subject throughout the study. Each amputee must have  $\geq 50\%$  reduction in all areas of qualifying RLP and PLP to be considered a success in the primary effectiveness endpoint analysis.

The primary endpoint of the study compares the proportion of subjects in Group #1 relative to that in Group #2 that achieve  $\geq 50\%$  reduction in all areas of qualifying post-amputation pain from baseline to the first 4 weeks of the home trial, examining the statistical superiority of proportion of clinical successes of Group #1 over the proportion of successes of Group #2. The post-amputation pain intensity scores will be determined for each subject by taking the mean of the daily average pain intensity (BPI-SF Question #5) reported in the 7-day diary at baseline compared to the mean score for the same region(s) of pain reported over the first 4 weeks of the home trial (*i.e.*, the average of all diary scores during this period). For each leg with leads, the average pain scores will only include the days when all leads are in place (e.g., if leads are placed in second leg during week 2 of home trial, then only the data from weeks 2-4 will be used). Data will be collected as described in the Schedule of Procedures (Appendix A).

**9.1.1 Baseline characteristics and changes in usage of medication affecting pain will be analyzed to determine how strong their relationships are with changes in pain intensity between baseline and EOT**

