### 9.1.5 Imputation of missing diary data during the home trial will be performed conservatively

Data missing from any day of diary during the first 4 weeks of the home trial will be imputed from baseline diary data, using the average pain score from the baseline week. Scores will only be imputed if recall data are unavailable and cannot be obtained.

[REDACTED]

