- Depression (Beck Depression Inventory (BDI-II)) at monthly intervals after start of therapy

The analysis of treatment effect on depression examines the statistical superiority of the mean percent improvement from baseline at monthly intervals of Group #1 relative to that of Group #2. In Group #1, the baseline BDI-II score (assessed at Visit 1) will be compared to the BDI-II score at each monthly interval after start of therapy. In Group #2, the baseline BDI-II score will be compared to the score at the end of the 4-week sham period. The null hypothesis is that there is no difference in mean percent improvement between the two treatment groups (*i.e.*, Group #1 at the monthly interval vs. Group #2 at end of sham period), versus the alternative hypothesis, that the mean percent improvements differ from one another. Testing will be conducted at the 0.05 level of significance.

- Analgesic usage

The analysis of treatment effect on analgesic usage will evaluate the change in opioid analgesic usage separately from the change in non-opioid analgesic usage (see Exploratory Measures, Section 9.4).

Changes in opioid analgesic usage will be calculated using morphine equivalent dosing (MED) to compare the mean percent change from baseline to the end of first 4 weeks in Group #1 relative to that of Group #2. Analysis will be conducted to determine if the mean change of Group #1 is statistically significantly greater than the mean improvement of the Group #2. The change in the opioid analgesic usage will be determined for subjects (who are receiving prescribed opioid medications at baseline) by taking the mean of the daily MED for the entries reported in the 7-day diary at baseline compared to the mean of the daily MED for the entries reported in the 7-day diary during the week before Visit 7 (*i.e.*, week 4 of home trial). The null hypothesis is that the mean change in MED is not significantly different in both groups, and the alternative hypothesis is that the mean change for the two groups differ.

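### BDI-II is tested on mean percent improvement with no readable minimum-baseline or zero-baseline rule; an ANCOVA on the baseline score already collected would avoid an undefined and low-baseline-dominated measure (minor, one secondary endpoint)

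*Combined protocol and SAP*

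**What the plan says.** Section 9.3 sets the depression endpoint on a percent scale: "The analysis of treatment effect on depression examines the statistical superiority of the mean percent improvement from baseline at monthly intervals of Group #1", with Group #2 as the comparator. The hypotheses follow: "The null hypothesis is that there is no difference in mean percent improvement between the two treatment groups", with a two-sided alternative at the 0.05 level. The denominator is the Visit 1 score. Group #1 is assessed at each monthly interval, Group #2 at the end of the 4-week sham period. No test statistic is named.

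On eligibility, the Synopsis excludes a "Beck Depression Inventory (BDI-II) score of" more than 20. This is an upper limit only. The matching limit in section 7.4.3 is blacked out.

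Neighbouring endpoints are protected. The primary endpoint uses "the region(s) of post-amputation pain with a 7-day average" of at least 4 at baseline, and the two durability analyses also require at least 4. Pain interference counts only qualifying regions, "defined as regions of RLP and PLP with an average baseline pain interference score" of at least 4. PDI is judged on a 10-point reduction, so it has no denominator.

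Baseline BDI-II is listed among the baseline characteristics in section 9.0: "These characteristics will be examined via a covariate analysis". Section 9.1.1 says that a list including it "will be examined via a covariate analysis to determine their influence on the primary outcome". Section 9.5 analyses secondary endpoints in both the ITT and per-protocol populations. The only readable imputation rule, section 9.1.5, concerns diaries: "Data missing from any day of diary during the first 4 weeks of the home trial will be imputed from baseline diary data".

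**The concern.** A percent change needs a denominator away from zero. Here the entry criterion confines the denominator to low values (20 or less) and sets no readable floor. Two things follow if the endpoint is the mean of each subject's own percentage.

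- A subject with a baseline of 0 has no percent improvement. That subject belongs to the ITT population once randomised and implanted, yet cannot enter the test as worded. Any exclusion or substitution would be chosen after data are seen.
- The measure is lopsided. Improvement stops at +100%, while worsening from a low baseline can reach several hundred percent. A clinically small rise in a subject who was hardly depressed can outweigh clear improvement in several others.

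The plan's pain and interference tests have a floor and are also responder tests, so an extreme percentage there counts only as one failure. BDI-II has no floor, no points criterion and no dichotomy.

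**Working it through.** **The plan's own figure.** No BDI-II power or variability is readable. The only stated power (over 90%, section 9.1.2) is for the primary endpoint, and its assumed success rates cannot be read, so there is nothing to reproduce for BDI-II.

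**Step 1: behaviour of the measure.** Percent improvement = 100 × (baseline − follow-up) / baseline.

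| Baseline | 2-point worsening |
|---|---|
| 0 | undefined |
| 1 | −200% |
| 2 | −100% |
| 5 | −40% |
| 10 | −20% |
| 20 | −10% |

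**Step 2: influence on a group mean.** Input: 27 per group (section 6.2). Shifts are relative to a subject with no change.

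- 1 to 4 scores −300%; shift = 300/27 = 11.1 points.
- 10 to 6 scores +40%; subjects needed to offset = 300/40 = 7.5.
- 20 to 16 scores +20%; subjects needed to offset = 300/20 = 15.
- 2 to 4 scores −100%; shift = 100/27 = 3.7 points, offset by 100/20 = 5 subjects going from 20 to 16.

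This step needs no distributional assumption, but it applies to raw means.

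**Step 3: how often a zero baseline might occur (assumed inputs).** The documents give no BDI-II distribution. Six were assumed: gamma-Poisson with mean 8, 10 or 12 and shape 3 or 5, truncated at 20. The share of zeros, p, is 0.24% to 2.1%. The chance of at least one in 54 is 1 − (1 − p)^54, which is 12% to 68%. Baselines of 1 to 4 make up 10% to 28% of subjects.

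**Step 4: power and type I error (assumed inputs).** Simulation with 27 per group, two-sided 0.05, both groups at week 4, 2,000 replicates per scenario. Follow-up = mean + slope × (baseline − mean), then less 3 points or multiplied by 0.7 in Group #1, plus normal error, rounded, floored at 0. Zero baselines were dropped for the percent tests. Ranges are over the six distributions.

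| Error SD, slope | Benefit | Welch t on percent | Mann-Whitney on percent | ANCOVA |
|---|---|---|---|---|
| 4, 0.7 | 3 points | 0.482–0.562 | 0.659–0.686 | 0.722–0.768 |
| 4, 0.7 | 30% | 0.211–0.490 | 0.388–0.687 | 0.530–0.830 |
| 4, 1 | 3 points | 0.580–0.624 | 0.661–0.680 | 0.723–0.739 |
| 4, 1 | 30% | 0.223–0.494 | 0.336–0.644 | 0.524–0.804 |
| 1 + 0.25 × baseline, 0.7 | 3 points | 0.849–0.984 | 0.850–0.982 | 0.800–0.932 |
| 1 + 0.25 × baseline, 0.7 | 30% | 0.532–0.676 | 0.643–0.788 | 0.745–0.867 |
| 1 + 0.25 × baseline, 1 | 3 points | 0.894–0.966 | 0.874–0.959 | 0.784–0.885 |
| 1 + 0.25 × baseline, 1 | 30% | 0.577–0.774 | 0.630–0.798 | 0.704–0.832 |

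ANCOVA leads in six of the eight settings and trails in the two with rising SD and a fixed 3-point benefit. There it is about 3 to 14 points behind the t-test and 4 to 12 behind Mann-Whitney. In the six favourable settings its lead over Mann-Whitney is 4 to 21 points. With baselines uniform on 10 to 20 and a 3-point benefit, ANCOVA minus t-test is −4 to +2 points.

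With no benefit, rejection rates are 0.026–0.054 (t), 0.041–0.058 (Mann-Whitney) and 0.044–0.064 (ANCOVA), with Monte Carlo standard error 0.005.

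**The case against.** - **Zero baselines may be rare or absent.** The documents do not give the scale minimum, and under the assumed distributions as little as 0.24% of subjects are at 0. The wording could also mean percent change of group means, for which an individual zero is harmless. This stands, so the undefined-value point is conditional on both readings.
- **The influence example is extreme and concerns raw means.** Fifteen subjects is the count at the highest admissible baseline; from 10 it is 7.5. Section 9.3 names no test, and the plan's only named two-sample test is Mann-Whitney, in the power section for the primary endpoint. On ranks, one extreme value has bounded influence. This stands, and it narrows the power gap.
- **The models partly build in the instability.** With slope 0.7 and mean 8, an untreated subject at baseline 1 has expected follow-up 8 + 0.7 × (1 − 8) = 3.1, or −210%. This stands: the power figures illustrate and do not predict.
- **A low-baseline rule alone would suffice.** It would cure the undefined values. In a separate set of runs (constant SD 4, slope 0.7, other baseline distributions), a minimum of 5 kept about 22 to 44 of 54 subjects and had lower power than ANCOVA in every scenario. Those runs did not cover the rising-SD case.
- **Covariate analysis is already planned.** Section 9.1.1 ties it to the primary outcome and section 9.0 is general. Neither specifies adjustment of the BDI-II test.
- **A rule may be blacked out.** Text is redacted in or near sections 4.4, 7.4.3, 9.0, 9.1.1 to 9.1.5 and 9.5. The claim is therefore only that none is readable.

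**Conclusion.** The point holds as a minor improvement to one secondary endpoint. The percent scale and the upper-limit-only entry criterion are in the readable text. The undefined value at 0 rests on an assumed scale minimum and on reading the endpoint as a mean of individual percentages. The dominance of low baselines needs only that low non-zero scores be admitted, and nothing readable excludes them. Its size in a group mean is 11.1 points for one subject going from 1 to 4.

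A reader might infer three stronger things that the evidence does not support:

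- That false positives are inflated. The simulated type I error shows no such effect.
- That the percent scale always costs power. The ordering reverses under rising error with a fixed benefit, and there is little difference if all baselines are 10 to 20.
- That the trial's main result is at risk. The primary endpoint has a baseline floor and is unaffected.

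**What to change.** Make the BDI-II test an ANCOVA of the follow-up score on group and baseline BDI-II score, at the visits the plan already names, and restate the hypotheses as a difference in adjusted mean score. Every subject with a baseline and a follow-up score can then be analysed, including any at 0. Report percent change descriptively, with a stated rule for a baseline of 0.

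The cost is SAP wording only: the Visit 1 score is already collected, and no subjects, visits or data are added. The downside is the possible loss of power in the reversed settings above. ANCOVA also does not resolve the comparison of Group #1 at later months with Group #2 at week 4. That is a separate matter, and the simulations cover only the comparison with both groups at week 4.
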